4.0 Scope

The scope is a post-market clinical study with adult users, in line with the scope of identified users as per the Usability Engineering File (DR010), with the Mobility+ system, which includes the 4 REF codes below.

REF code	Product
Mob1- 440	Mobility+ with 440mm Giving Set
Mob1-700	Mobility+ with 700mm Giving Set
Mob1-1000	Mobility+ with 1000mm Giving Set
Mob1-1900	Mobility+ with 1900mm Giving Set

The scope includes use of the Mobility+ via filling the system from feed poured into a container (See IFU Filling Method A) and excludes filling the system from a ready to hang feed bag (Filling Method B, IFU).

ISO 14155 principles are applied in part to this protocol, to suit the clinical developmental stage of Mobility+ and study design, in line with Annex I I.7 ISO 14155:2020.

 
Rockfield MEDICAL DEVICES
	
Safety and Effectiveness of A Novel Enteral Feeding System: Prospective Study Protocol Page 10 of 49
	
NCT06173063

---	---	--------------------

6.0 Appendix List

- Appendix 1:** Screening Log
- Appendix 2:** Screening questionnaire
- Appendix 3:** Demographics questionnaire
- Appendix 4:** Participant perspectives baseline survey
- Appendix 5:** QoL survey
- Appendix 6:** Phone communication check sheet – Trial days
- Appendix 7:** Participant perspectives outcome survey
- Appendix 8:** Phone communication check sheet (Study Day 7 and 14)
- Appendix 9:** Adverse event classifications
- Appendix 10:** Adverse events logging method
- Appendix 11:** Participant familiarization training
- Appendix 12:** Participant familiarization training record
- Appendix 13:** Operator training record
- Appendix 14:** Evidence of expert review

7.0 Definitions

Term	Description
User	Person interaction with medical device
Operator	Operators are study staff who have self-trained in the use of Mobility+ and who have received training in the execution of this Protocol by the sponsor, Rockfield Medical Devices. Study staff in this study comprise advanced nursing practitioners, registered dietitians, researchers and principal investigator.
Participant	Individual who is or becomes a participant in a clinical investigation, as a recipient of the investigational device. Note that 'participants' in this study are users of the device who are being enterally fed in clinical settings or who are feeding at home (as per Usability Engineering File DR010).
Investigational medical device	Medical device being assessed for clinical performance, effectiveness, or safety in a clinical investigation
Clinical effectiveness	Achievement of a clinically significant intended result in a defined portion of the target population when the investigational medical device is used within its intended uses and according to its instructions for use, as determined by documented scientific evidence
Malfunction	Failure of an investigational medical device to perform in accordance with its intended purpose when used in accordance with the instructions for use
Principal Investigator	Qualified person responsible for conducting the clinical investigation at an investigation site
Use error (ISO 14155:2020)	User action or lack of action while using the medical device that leads to a different result than that intended by the manufacturer or expected by the user. Note: Use error includes inability of the user to complete a task.
Adverse event (AE) (ISO 14155:2020)	Untoward medical occurrence, unintended disease or injury, or untoward clinical signs (including abnormal laboratory findings) in subjects, users or other persons, whether or not related to the investigational medical device and whether anticipated or unanticipated
Serious adverse	adverse event that led to any of the following

effect (SAE)	
 a) Death b) Serious deterioration in the health of the subject, users, or other persons as defined by one or more of the following: 
 1) A life-threatening illness or injury, or 2) A permanent impairment of a body structure or a body function including chronic diseases, or 3) In-patient or prolonged hospitalization, or 4) Medical or surgical intervention to prevent life-threatening illness or injury, or permanent impairment to a body structure or a body function, c) Fetal distress, fetal death, a congenital abnormality, or birth defect including physical or mental impairment
Adverse device effect (ADE)	Adverse event related to the use of an investigational medical device.
Serious adverse device effect (SADE)	Adverse device effect that has resulted in any of the consequences characteristic of a serious adverse event
Unanticipated serious adverse device effect (USADE)	
Serious adverse device effect which by its nature, incidence, severity or outcome has not been identified in the current risk assessment
 
Note: Anticipated serious adverse device effect (ASADE) is an effect which by its nature, incidence, severity or outcome has been identified in the risk assessment

Serious public health threat	Serious public health threat, means an event which could result in imminent risk of death, serious deterioration in a person's state of health, or serious illness, that may require prompt remedial action, and that may cause significant morbidity or mortality in humans, or that is unusual or unexpected for the given place and time
Stock-Keeping Unit (SKU)	A Stock-Keeping Unit is a number (and sometimes letters) that is assigned to a product for the purpose of inventory management and ease or tracking

	
Safety and Effectiveness of A Novel Enteral Feeding System: Prospective Study Protocol Page 13 of 49
	
NCT06173063

---	---	---

8.0 Methods

8.1 General Methodology

The study duration will allow 25 participants to use the Mobility+ system for their feeding sessions over the course of 14 consecutive days, following an initial 7-day period where participants have time to trial and get used to the new system. As determined by the PI, five to seven pre-intervention days (During 'Trial days' 1 to 7), with a minimum of 5, is time to allow participants to become familiar with a new feeding system (i.e., Mobility+) and 14 days (Study Day 1 through Day 14 inclusive) is the time required to effectively assess safety and effectiveness of Mobility+ (as outlined in **Appendix 8**).

The environment is Mayo Clinic Setting at study outset for the clinic visits where participants will be screened, consented, and enrolled. Participants' homes are the setting for the 21-day study duration.

Mobility+ Devices will be built by a process detailed within a Mobility+ Work Instruction, from within a quality management system. The work instruction will be in place at the time of Mobility+ production runs occurring before execution of this protocol.

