3.0 Purpose

The purpose is to evaluate the safety and effectiveness of Mobility+ enteral feeding system via this initial post-market study (510k clearance number K222678) in adults, a subset of the intended use population. This evaluation will be conducted in a prospective, single arm, non-randomized clinical study.

Hypothesis and Objectives

The study hypothesis is that Mobility+ meets its intended use, safely. The objectives are to evaluate the below primary and secondary endpoints, through execution of this protocol:

Endpoint	Detail	How it will be measured
Primary: Safety and Effectiveness of Mobility+	Evaluate participants who have received familiarization training can use device, according to IFU, to allow delivery of liquid nutrition to their feeding tube, in a real-life setting (home), safely (i.e. can execute critical device use tasks to allow feeding, without serious adverse events) and with effectiveness (i.e. using Mobility+ for the majority or all of their feeding sessions i.e. two daily feeds, minimum)	Phone communication and checklist (Appendix8)

Secondary: Usability of Mobility+	Evaluate Participant perspectives on mobility, ease of use and tolerance, with their current feeding system(s) and Mobility+	Participant perspectives surveys: Baseline (Appendix 4) End of study (Appendix 7)
	Evaluate changes in participant Quality of Life (QoL)	QoL survey at baseline (Appendix 5) and QoL question at end of study (Appendix 7)
	Estimate if participants consume similar average volume (and kcals) of feed/day during the study, compared to baseline	Collect descriptive data on estimated average feed volume and kcals consumed at baseline (Appendix 3) and at end of study (Appendix 8)

The outcome will be presented in a study report.

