8.11 Phone Communication

1. Pre-intervention phase – Trial days

Phone communication on **Trial Days 1; 3 and 5**: Participant is contacted by telephone to ensure the participant is becoming familiar with using the device including the most appropriate giving-set tubing SKU. (**Appendix 6**).

2. Intervention phase – Study days

- Phone communication - Study **Day 7**: Participant is contacted by telephone to ensure they are successfully and safely feeding with an appropriate tubing SKU, and check compliance and calorie intake (**Appendix 8**).
- Phone communication -Study **Day 14**: Participant is contacted by telephone to ensure participant is successfully and safely feeding with an appropriate tubing SKU, and check compliance and calorie intake. Operator also evaluates self-perceived wellbeing, mobility, wearing methods, and longer-term device use wishes (**Appendix 8**) Administer participant perspectives outcome survey, including question on QoL (**Appendix 7**)

Note: Regarding disposal – as per IFU, devices are disposed of alongside normal waste.

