Appendix 5**QoL survey**

(Operator asks the Participant these questions)

Reference: Elfadil OM, Patel A, Abdelmagid M, et al. 1117929 - Mental Health Among Enteral Feeding Patients and Caregivers: Is Home Enteral Nutrition Overwhelming? Nutrition and Metabolism Research Oral Paper Session Abstracts. ASPEN Nutrition Science & Practice Conference: March 26-29, 2022 (Seattle, WA). JPEN J Parenter Enteral Nutr. 2022 Mar;46 (S1) <https://aspenjournals.onlinelibrary.wiley.com/doi/full/10.1002/jpen.2344>

Rate your quality of life	Excellent	Good	Neutral	Bad	Very Bad

Appendix 6
Phone Communication check sheet – Trial days

(Operator to use this check sheet to log tubing SKU and changes)

Tubing SKU check								
Trial Day 1: SKU that participant is using: 
 
 440mm RED 	700mm BLUE 	1000mm GREEN 	1900mm WHITE 	
 
					440mm RED 	700mm BLUE 	1000mm GREEN 	1900mm WHITE 
440mm RED 	700mm BLUE 	1000mm GREEN 	1900mm WHITE 					
Select one: 		Stay on this SKU 						
		Trial _____ SKU 						
Reason for changing: <hr/>								
Trial Day 3: SKU that participant is using: 
 
 440mm RED 	700mm BLUE 	1000mm GREEN 	1900mm WHITE 	
 
					440mm RED 	700mm BLUE 	1000mm GREEN 	1900mm WHITE 
440mm RED 	700mm BLUE 	1000mm GREEN 	1900mm WHITE 					
Select one: 		Stay on this SKU 						
		Trial _____ SKU 						
Reason for changing: <hr/>								

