		

How strongly do you agree with the following statement? I would like to use the Mobility+ again.

Strongly Agree	Somewhat Agree	Neutral	Somewhat Disagree	Strongly Disagree
				

If you would like to use Mobility+ again, how often would you like to use it?

Every Day	Every Week	Every Month
		

Think about your overall wellbeing if you used Mobility+ for SOME/ALL of your tube feeding needs, in the long term. How would your wellbeing be then, compared to now?

Much Better	Somewhat Better	About the Same	Somewhat Worse	Much Worse
				

Would you pay out of pocket for the Mobility+?

YES	NO
	

How did you choose to wear the Mobility+ system?

- Crossbody bag**
- Handbag**
- Backpack**
- In clothing**
- Clipped onto belt/clothing**
- Other (Detail):**

Appendix 8

Appendix 8 - Phone communication check sheet (Study Day 7 and 14) - (Operator asks the Participant these questions)

Day 7

Day 7			
Questions:	Answers:		
Day 7 Safety & Effectiveness Check			
Are you able to use Mobility+ to successfully and safely provide enteral feeding?	 YES  NO		
Day 7 Compliance & Calorie Intake Check			
Consider your feed intake over the last 3 days (i.e. Study day 4, 5, 6).			
Questions:	Answers:		
What volume of enteral nutrition did you consume on average per day (i.e. over 24 hr)?	Volume Mobility+mls		
How many hours did you typically infuse for, on average/day? hours minutes		
How many feedings did you intend to take using Mobility+ , on average / day?feedings		
How many feedings were you able to take using Mobility+ , on average / day?feedings		
What was the average volume of enteral nutrition that you consumed per feeding with Mobility+?mls		
What time of the day did you provide feedings with Mobility+?	Morning  Afternoon  Evening  Night-time 		
Operator facing question: On average, did the participant take at least two daily feeds with Mobility+? If no, why not?	 YES		
	 NO		
Day 7 Tubing SKU check			
Study Day 7:			
SKU that participant is using:			

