Serious	Serious adverse event (SAE) ^b (3.45)	Serious adverse device effect (SADE) (3.44)	
		Anticipated	Unanticipated
		Anticipated serious adverse device effect (ASADE) ^c (3.1, Note 1 to entry)	Unanticipated serious adverse device effect (USADE) (3.51)

^a Includes all categories.
^b Includes all categories that are serious.
^c Includes all categories that are related to the device or the investigational procedure.

[figure not shown]

Figure F.1 — Adverse events categorization chart

The flowchart below on device deficiencies should only be used in case the device deficiency is not associated with an adverse event.

[figure not shown]

Figure F.2 — Device deficiency categorization chart

Appendix 10
Adverse Events Logging Method

The PI undertakes to report serious matters in a timely manner (within 24 hours) to the sponsor including details on the below:

- Participant ID
- Operator ID
- Incident date and time
- Incident details Incident category
- PI assessment details
- Determination
- Action
- Time PI reported assessment to Sponsor

Appendix 11

Participant Familiarization Training

This familiarization training matches typical training provided for new users of new enteral feeding systems on discharge and consists of a 1:1 demonstration of the system, including bringing attention to the labelling of the system, to minimize the potential for user errors to occur during unsupervised home use. Participants will attend a short 1:1 training session with a trained operator where they will be trained on Filling Method A (Filling from feed poured into a container), flushing, feeding, and wearing, as below. The setting will be a room in a clinical environment.

- Provide participant with Instructions for Use (IFU) booklet, a Mobility+ feeding pouch, giving set tubing, filling-set tubing, an ENFIT syringe and a cross-body bag
- Inform participant of the option to consult an instructional video, which can be accessed via smart device by scanning QR code on the IFU

Filling

- Demonstrate **Filling Method A** steps by filling a pouch with some water or formula.

Feeding

- Demonstrate 'feeding' by letting the Feeding Pouch (with giving-set attached) deliver some of its contents into a beaker.
- Explain the Feeding pouch deflates and reduces in weight as liquid feed is delivered, and the feed session is finished when no more liquid flows out of the tubing

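### The primary endpoint asks about home use after familiarization training, but it is scored only after a 5–7 day supported run-in, and no rule counts a stop during that run-in as a failure

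*Protocol*

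**What the plan says.** **The question.** The primary endpoint in protocol section 3.0 is to "Evaluate participants who have received familiarization training can use device, according to IFU, to allow delivery of liquid nutrition to their feeding tube". The setting is the home. Safe means completing the critical tasks with no serious adverse event (SAE). Effective means at least two feeds a day with the device. No time window is written into the endpoint.

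**The instrument.** Section 3.0 names one source, "Phone communication and checklist (Appendix8"), and that appendix is headed "Phone communication check sheet (Study Day 7 and 14"). Section 8.1 says that "14 days (Study Day 1 through Day 14 inclusive) is the time required to effectively assess safety and effectiveness of Mobility" and points to the same appendix.

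**What comes before scoring.** Familiarization training is one short one-to-one clinic session. Appendix 11 says "This familiarization training matches typical training provided for new users of new enteral feeding systems on discharge". Table 4 puts first clinical use in the Trial Days. Section 8.11 schedules calls on Trial Days 1, 3 and 5, with this stated purpose: "Participant is contacted by telephone to ensure the participant is becoming familiar with using the device including the most appropriate giving-set tubing SKU". Section 8.7 has operators adjust the giving-set SKU during this period until the best fit is found.

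**What is recorded before scoring.** The instruction on Appendix 6 is "Operator to use this check sheet to log tubing SKU and changes". The form holds the SKU in use, whether to stay or change, the reason for a change, one admission question at Trial Day 5, and a reminder of the study start. It has no item on successful or safe use, task completion or number of feeds.

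**Stopping.** Section 8.13 ends participation after hospitalization for any reason, in the trial days or the study days. Section 7.0 lists in-patient hospitalization among the criteria for an SAE.

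**Results.** SAP 3.0 gives 19 participants included. SAP 7.0 reports on 17: 17 (100%) fed successfully and safely, and 16 (94.1%) reached two daily feeds. The enrollment table in SAP 6.0 also uses 17.

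**The concern.** The population in the endpoint is defined by the clinic training session, so its natural starting point is the first home use after that session. The score starts later, once users have practised at home, spoken to an operator up to three times and had their flow rate tuned. Those are two different questions: whether trained first-time users can use the device, and whether users who have come through a supported run-in can use it.

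The difference matters for people who do not get through. A participant admitted to hospital on Trial Day 4 has an SAE by the protocol's own definition and so fails the safety part of the endpoint. Section 8.13 also ends that person's participation, so Appendix 8 is never completed. The same happens to someone who gives up in the first week because the pouch cannot be filled or the feed is not tolerated. With no counting rule, such a person can drop out of both numerator and denominator, and the study can report 100% safe and successful use. Section 8.3 calls this a first-in-human study, so the first days of use are of particular interest.

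**Working it through.** **1. The plan's own figures.** Section 8.3 wants data on 20 participants and expects about 20% dropout: 20/(1 − 0.20) = 25, which matches the planned enrollment. SAP 3.0: 548 − 493 − 11 − 25 = 19, which also matches. No test, threshold or power calculation is given for the primary endpoint, so there is none to reproduce.

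**2. Share of device use that is not scored.** Section 8.1 gives 5 to 7 trial days followed by 14 study days.
- 5-day run-in: 5/(5 + 14) = 5/19 = 26.3%
- 7-day run-in: 7/(7 + 14) = 7/21 = 33.3%

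The period includes all first use. Sections 8.1 and 8.11 call it pre-intervention, while Table 4 places it inside a 21-day intervention phase (7 + 14 = 21). The labels need to be reconciled.

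**3. Can Appendix 8 recover a trial-day failure?** No. Its success-and-safety item is in the present tense. Its feeding items look back three days (Study Days 4–6 and 11–13). A participant who has already stopped does not complete it.

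**4. Direction of the effect.** Let s be the successes among n participants scored, and m the trial-day stops that should count as failures. The reported rate is s/n, and the rate from first use is s/(n + m). Since m ≥ 0, s/(n + m) ≤ s/n. The reported rate is therefore either right (m = 0) or too high.

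**5. Possible size.** The number of trial-day stops is not given. Taking the 17 reported as a subset of the 19 included, at most 19 − 17 = 2 participants can have left unscored. Intervals are exact (Clopper–Pearson) 95%.

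| Assumption | Successful and safe | Two daily feeds |
|---|---|---|
| Neither of the two counts as a failure | 17/17 = 100% (80.5–100) | 16/17 = 94.1% (71.3–99.9) |
| One counts, the other is outside the denominator | 17/18 = 94.4% | 16/18 = 88.9% |
| Both count as failures | 17/19 = 89.5% (66.9–98.7) | 16/19 = 84.2% (60.4–96.6) |

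**The case against.** The best defence is that the run-in is open and reasoned. The investigator set it, participants are told about it, and it serves to move from a deliberately slow starting SKU to a suitable one. Performance after fitting is a legitimate question. That stands, and it is why the run-in need not be removed and Trial Day 1 need not become the only starting point. It does not remove the mismatch with the wording of section 3.0, or supply the missing counting rule.

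Several stronger readings are tempting, and the documents do not support them.

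- **That the run-in is an enrichment step and the result is biased.** No success or tolerance test governs entry to Study Day 1. The only stated removal rule, hospitalization, applies equally in the study days. A participant who struggles but stays is still scored. Upward bias is possible but not shown.
- **That early safety events are lost.** Under section 8.13 adverse events that become known are assessed, and under section 10.0 serious matters are reported within 24 hours. The SAE phrase in section 3.0 has no time window, so no text excludes trial-day SAEs. What is missing is a rule that carries them into the primary result.
- **That the trial-day form captures nothing clinical.** Appendix 6 asks the reason for each SKU change, where intolerance could appear, and asks about admission at Trial Day 5. Appendix 8 as printed has no adverse event item either, so that gap is not peculiar to the run-in.
- **That several run-in failures could be hidden, given 25 planned and about 20% expected dropout.** The SAP's 19 included and 17 reported cap unscored departures at two.
- **That the two missing participants failed in the run-in.** Neither the timing nor the reason is given.

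**Conclusion.** The point holds as a mismatch between the endpoint as worded and the endpoint as scored, together with a missing counting rule. Between 26% and 33% of device-use days, including all first use, lie outside the scored window. A trial-day stop for device, tolerance or SAE reasons would not count against the device, so the rate can only be unchanged or too high.

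Whether it is too high in this study cannot be settled from the documents. The bounds are 100% if neither unreported participant was a failure and 89.5% if both were. The lower bound assumes that both had a first clinical use and stopped for a qualifying reason. It lies inside the interval around 17/17 (80.5–100), so the numerical effect is modest beside the sampling error. The more important consequence is for interpretation: as presented, the 100% in SAP 7.0 reads as a result for trained first-time users, and the documents support it only for those who reached the Appendix 8 checks after a supported run-in. It should be corrected, and the data needed were to be logged.

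**What to change.** Keep the run-in and change the accounting.

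1. **Primary result.** Report it for everyone with a first clinical use, expected to be up to the 19 included. Count a trial-day stop for device, tolerance or SAE reasons as a failure. The sources are the withdrawals with reasons logged under section 8.7 and the adverse events recorded under sections 8.13 and 10.0. List stops for other reasons separately. This concerns counting only and takes no position on the hospitalization rule.
2. **Labelling.** In section 3.0 and SAP 7.0, state that the Study Day 1–14 result applies after a 5–7 day supported run-in, and show it second.
3. **Missing participants.** State when and why the two included but unreported participants left, and whether each had a first clinical use. If this cannot be established, show 17/17 and 17/19 side by side and limit the SAP 7.0 statement to users who reached the Appendix 8 checks.
4. **If the study were run again.** Add the success-and-safety item from Appendix 8 and an adverse event item to the three existing Trial Day calls.

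The cost is one extra table and a possibly lower stated rate. Item 4 would add two questions to calls that are already scheduled.
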